## 5.6 Adverse Events

Adverse events were collected for both MANTA related AEs and non-MANTA related AEs. All events that occur during or after the procedure will be summarized (events prior to treatment will not be included) as identified via "Phase of study in which AE developed" on first page of AE eCRF.

The CEC will adjudicate procedure and device relatedness. Classifications of Definite, Probably, Possible and Unknown will be considered related. Note that a template of the tables figures listings (TFL) template was developed for how to present these data.

1. MANTA related AEs will be summarized summarizing the count and % of patients experiencing one or more events.
  - a. An overview (overall, VARC-2 Major femoral vascular complication, VARC-2 Minor femoral vascular complication, device related serious AE, device related AE, and any unanticipated serious adverse device effect (USADE)).
  - b. Summary of MANTA related:
    - i. VARC 2 Major femoral vascular complication and definition element
      1. Overall
      2. CEC procedure related
      3. CEC device related
    - ii. VARC 2 Minor femoral vascular complication and definition element
      1. Overall
      2. CEC procedure related
      3. CEC device related
    - iii. VARC 2 Major femoral complication and definition element by timing
      1. Overall
      2. CEC procedure related
      3. CEC device related
    - iv. VARC 2 Minor femoral complication and definition element by timing
      1. Overall
      2. CEC procedure related
      3. CEC device related
    - v. AES by MedDRA coding System Organ Class (SOC) and Preferred Term (PT)
      1. Overall AE
      2. Investigator determined if CEC not available related AE
      3. CEC procedure related AE
    - vi. SAES by MedDRA coding System Organ Class (SOC) and Preferred Term (PT)
      1. Overall SAE
      2. Investigator determined if CEC not available related SAE
      3. CEC procedure related SAE
  - c. Listings will be generated
    - i. MANTA related (investigator determined):
      1. patient ID, onset (days post proc), event, MedDRA SOC/PT, description of treatments/interventions, status (outcome), severity, seriousness, and MANTA relatedness (unknown, possible, probably or definite), and CEC VARC2 determination and proc/device relatedness.

- ii. Not MANTA related (reduced list due to reduced data collection):
  1. Patient ID, onset, MedDRA SOC/PT, status, and seriousness.
  2. Long-term MANTA AEs (Day 31-12M) will be summarized by seriousness for subjects that participated in the extended follow-up for the whole cohort, the 30 day cohort and the 12M cohort.
  3. Death summaries: any subjects that died will summarized by cause of death as adjudicated by CEC. Additionally, all AEs for those subjects will be listed.

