Interim analysis may be performed throughout the duration of the registry.

8.5. *Minimum and Maximum Patient Recruitment for Analysis*

Study enrollment will be competitive. There is no minimum or maximum number of patients that can be enrolled per site.

8.6 *12M Follow-Up Analysis and Minimization of Bias*

A minimum of 100 and up to a maximum of 120 subjects will be re-enrolled into the registry to complete the 12M follow-up visit. Bias will be minimized by contacting subjects who were treated within a specific timeframe designated by the Sponsor (for example, September 2018 to July 2019). Sites will be extended an invitation to participate in the study if they have enrolled at least 10 subjects within the identified timeframe in order to justify study costs incurred to keep the site open, submit amendments to the appropriate ethics committee, bandwidth of the site research team, etc.

The subset followed to one year is expected to be similar to the overall cohort in baseline patient characteristics. Baseline data for the 12M subset will be analyzed and compared to the overall cohort to demonstrate that the subset is representative of the overall cohort. If there are differences in the baseline characteristics of the subset and the overall cohort, these will be further evaluated and assessed as to their potential impact on the 12M results.

To test for generalizability of 12-month outcomes, patients undergoing 12-month follow-up will be compared to patients not undergoing 12-month follow-up in a pre-specified analysis of baseline demographics, clinical characteristics, procedural variables and in-hospital/30-day end-point outcomes.

Only AEs related to the MANTA access site or the ipsilateral leg will be collected at the 12M visit. AE data from the 12M visit will be analyzed separately from the primary safety endpoint, as 12M data will only be available on a subset of the study cohort and the primary safety endpoint is events through 30-days.

9. Adverse Events

9.1. *Definitions*

Refer to Section 4 for the definitions of the following terms associated with adverse events:

- Adverse Event
- Adverse Device Effect
- Device Deficiency
- Serious Adverse Event
- Serious Adverse Device Effect
- Unanticipated Serious Adverse Device Effect

9.2. *Potential Adverse Events and Adverse Device Effects*

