The primary responsibilities of the CEC over the course of the study are to review and refine serious adverse event definitions, and to review and adjudicate serious adverse events.

The CEC will determine if each reviewed adverse event meets the definition of a VARC-2 Major femoral vascular complication or a VARC-2 Minor femoral vascular complication or neither definition. For each AE reviewed, the CEC may also adjudicate its device-relatedness. Any analysis of the primary and secondary safety endpoints will be based on CEC-adjudicated data.

AEs identified in the subset of patients completing the 12M extended follow-up will not be adjudicated,

Essential Medical, Inc. Protocol
No. PSD-212 Rev.C
as the safety endpoints are through 30 days.

10. Medication

There are no prohibited medications for this clinical investigation.

Only the following medications will be recorded on the CRF: Aspirin, Clopidogrel, Vitamin K Antagonists, and NOAC's (eloxaban, rivaroxaban, dabigatran, apixaban) at baseline through 30-day follow-up, inclusive of medications given in the cath lab.

11. Vulnerable Population

The intended patient population of this post-market registry does not meet the criteria of vulnerable population as defined in ISO 14155, Section 3.44.

12. Outsourcing

The Sponsor may transfer some duties and functions related to the clinical study, such as monitoring, data management, etc. to an external organization (such as a contract research organization or individual contractor). When outsourcing does occur, the ultimate responsibility for the quality and integrity of the clinical study will reside with the Sponsor. All requirements applying to the Sponsor will also apply to the external organization inasmuch as this organization assumes the clinical study related duties and functions of the Sponsor.

13. Data Management

The Sponsor/designee will be responsible for data handling. The Sponsor will be responsible for compiling and submitting all required reports to governmental agencies.

Data will be analyzed by the Sponsor/designee and may be transferred to the Sponsor's locations outside of Europe.

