Adverse Events		X	X	X	X	X	X	X	X

1. Medications (only Aspirin, Clopidogrel, Vitamin K Antagonists and, NOAC's: [eloxaban, rivaroxaban, dabigatran, apixaban] will be collected)
2. Screening Visit CT Scan to assess both limbs for presence/absence of calcium, atherosclerotic disease, tortuosity, and acceptable flow rates.
3. Prior to MANTA closure, record ACT and systolic BP (per contraindications BP<180; recommend ACT below 250 seconds prior to closure)
  - \* #2 CT Angiographic Scan and #4 Post MANTA femoral angiogram are required in cohort 1
4. Post-MANTA closure, perform target (ipsilateral) common femoral angiography from contralateral access site to ensure patency into the ipsilateral common femoral artery
5. A subset of study enrollment, 100-120 subjects at up to 7 sites, will complete the 12M follow-up visit.

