## 4 Sample Size Requirements

Up to 500 subjects are considered a meaningful sample size to assess real-world use of the MANTA device. There is no statistical basis for the sample size. Up to 20 sites will be included in the trial.

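### SAP 5.6 sets no end of observation for the MANTA-related AE tables or the death summary, so 30-day capture in everyone is pooled with 12-month capture in a re-consented subset

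*SAP*

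**What the plan says.** **Scope of the tables.** The lead-in to SAP 5.6 reads "All events that occur during or after the procedure will be summarized (events prior to treatment will not be included". This sets a start of observation but no end. Item 1 counts patients, and gives the percentage, with one or more MANTA-related AEs. It covers an overview (1.a), VARC-2 tables (1.b.i–iv, including "VARC 2 Major femoral complication and definition element by timing") and MedDRA tables for AEs and SAEs (1.b.v–vi). The MedDRA tables have a row labelled "Investigator determined if CEC not available related AE". Item 3 says that "any subjects that died will summarized by cause of death as adjudicated by CEC". Neither item gives an onset limit or a denominator. SAP 6 adds that all available data go into any summary for a subject with a procedure attempt.

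**Late events.** SAP 5.6 item 2 asks for a separate summary of MANTA AEs from Day 31 to 12M. It names subjects in the extended follow-up, but then asks for results in the full cohort, the 30-day cohort and the 12M cohort. SAP 5.5 item 4 starts the late period at day 38.

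**Who is observed, and how.** Under Protocol 7.7, subjects exit after the 30-day follow-up. Some are contacted again and sign a consent addendum for the 12M visit. The footnote to SAP Table 1 says: "A subset of study enrollment, 100-120 subjects at up to 7 sites, will complete the 12M follow-up visit". Protocol 8.6 says: "Only AEs related to the MANTA access site or the ipsilateral leg will be collected at the 12M visit". Protocol 9.7 says: "AEs identified in the subset of patients completing the 12M extended follow-up will not be adjudicated".

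**Limits already in place.** SAP 5.2 and 5.3 hold the major and minor complication endpoints to 30 days. Protocol 8.6 keeps 12M AE data apart from the primary safety endpoint.

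**The concern.** Ascertainment changes at the 30-day exit. Before it, every subject is observed and AEs that the investigator considers possibly, probably or definitely device-related go to the CEC. After it, only the re-consented subset is observed, at one visit, without adjudication.

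A table with no closing date takes in both periods. Its percentage of patients with an event then depends on how many subjects happened to re-enrol as well as on the device. A reader of the post-market report would probably take the figure as a 30-day rate, or as the registry's overall rate, and it is neither.

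Deaths have a further problem. Item 3 presupposes a CEC-adjudicated cause, which is not planned for 12M events, and the 12M visit does not look beyond the access site and the leg. Subjects had to be alive to be contacted and re-consent, and the plan provides no capture of later deaths among those who did not re-enrol.

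**Working it through.** The study is descriptive and the plan gives no figure for this point, so there is nothing to reproduce. The check is how far a table without a cut-off departs from a 30-day table.

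**Inputs**
- N = 500, the ceiling in SAP 4 ("Up to 500 subjects are considered a meaningful sample size to assess real-world use of the MANTA device"). Actual enrolment is not stated.
- m = 100 to 120 subjects with a 12M visit.
- Observation: 30 days for all, and 365 − 30 = 335 further days for the subset. Full follow-up is assumed.
- q = share of 12M subjects whose first MANTA-related AE falls after the early period. The documents give no value; I assume 1%, 2% and 5%.
- p = 30-day risk, assumed to be 4% for illustration.

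**Split of subjects.** 500 − 120 = 380 to 500 − 100 = 400 subjects have 30-day capture only. The subset is 100/500 = 20% to 120/500 = 24%.

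**Person-time**
- All subjects to Day 30: 500 × 30 = 15,000 days.
- Subset after Day 30: 100 × 335 = 33,500 days, or 120 × 335 = 40,200 days.
- Late share: 33,500/48,500 = 69%, or 40,200/55,200 = 73%.

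**Effect on the reported percentage.** Pooled value = p + (m/N) × q. The 30-day risk is p and the 12-month risk is p + q. The last column is 1 − (1 − q)^m.

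| Assumed q | Points added, (m/N) × q | Pooled value (p = 4%) | 12-month risk, p + q | Chance of at least one late event |
|---|---|---|---|---|
| 1% | 0.20–0.24 | 4.2% | 5% | 63–70% |
| 2% | 0.40–0.48 | 4.4–4.5% | 6% | 87–91% |
| 5% | 1.0–1.2 | 5.0–5.2% | 9% | over 99% |

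If q is instead read as the risk among subjects event-free at 30 days, the 12-month risk is p + (1 − p) × q = 4.96%, 5.92% and 8.8%. In every row the pooled value lies between the 30-day and the 12-month risk and estimates neither.

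**Does another passage close the window?**
- Item 2 creates a late table but does not say that its events leave item 1.
- Protocol 8.6 separates 12M data from the primary safety endpoint only.
- SAP 6 points towards inclusion.
- Where the authors wanted a window they wrote one: SAP 5.2, 5.3, procedure success, and 5.6 item 2. Items 1 and 3 have none.

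**The case against.** The strongest reply is that late data already have a place (SAP 5.4, 5.5 item 4 and 5.6 item 2), so item 1 followed by a long-term item 2 reads naturally as early then late. Each AE also carries a study-phase field, and the table template, which is not in the documents, may set the windows. This is a fair reading of intent. It does not change the wording of 5.6 and SAP 6, and the SAP itself should state the window.

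Several stronger readings are tempting, and the documents do not support them:
- **That every post-procedure event is pooled.** Item 1 is restricted to MANTA-related AEs; unrelated events appear in 5.6 only as a listing. The leg-only scope at 12M is close to item 1's own scope, so it matters mainly for deaths.
- **That the VARC-2 tables, including those by timing, are mixed.** SAP Appendix 1 and the CEC remit in SAP 3 tie major and minor complications to 30 days, and 12M events receive no CEC classification. Against that, SAP 5.4 applies the same terms after 30 days. The point is ambiguous, and the timing categories are not shown.
- **That the investigator fallback shows an intent to admit late events.** It has an ordinary 30-day use, because SAP 3 withholds certain small or unsized hematomas and minor bleeds from the CEC. It still leaves a route by which unadjudicated late events could count as related.
- **That a pooled death percentage is planned.** Item 3 states no percentage.
- **That the distortion is large.** Nothing in the documents supports a high late risk. The 69–73% share of person-time would translate into events only if risk stayed roughly constant, and access-site complications may well cluster early.

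**Conclusion.** The gap is real and limited. As written, the MANTA-related AE overview and the MedDRA AE and SAE tables (items 1.a and 1.b.v–vi) pool two observation periods, and the death summary has no coherent time horizon or source of adjudication. Item 2 adds to the difficulty by requesting Day 31–12M results in cohorts whose exited members have no planned observation then.

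The size rests on assumed late risks, with 500 enrolled and full follow-up: 0.2–0.5 points at 1–2%, and 1.0–1.2 points at 5%. The case for change is that the percentage has no defined meaning, more than that it is badly wrong.

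A reader might infer that the 30-day primary and secondary safety results are contaminated. They are not: SAP 5.2 and 5.3 and Protocol 8.6 protect them.

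**What to change.** In SAP 5.6 and the matching table shells:

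1. Limit items 1 and 3 to events with onset up to each subject's 30-day follow-up or, if there was none, the first study exit. Use all subjects with a procedure attempt as the denominator, and close any timing categories at the same point. A fixed cut at Day 30 would not do. The visit window is ±7 days, so Day 31–37 events in subjects outside the 12M subset would move to a table whose denominator excludes them.
2. Report later events only in item 2, with the 12M participants as the sole denominator. Drop the full-cohort and 30-day-cohort versions. Label the table as investigator-reported, not adjudicated and limited to the MANTA leg.
3. List later deaths individually, and state that capture after the 30-day exit is incomplete.
4. Use one start of the late period, consistent with the cut-off in step 1, in both 5.5 item 4 (now day 38) and 5.6 item 2 (now Day 31).
5. Assign events first reported at the 12M visit with an incomplete onset date by the visit at which they were reported. SAP 6 replaces a missing month with the procedure date, which would put such an event in the early table.

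The cost is a few sentences, an onset-date filter and slightly lower percentages in the main tables. Those tables should be titled as running through the 30-day follow-up, because that window can extend a few days past the 30 days used for the endpoints in SAP 5.2 and 5.3.

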## 6 Data Conventions and Missing Data

No imputations will be made for missing data. All available data will be summarized for any summary provided the subject has a procedure attempt.

If an onset date for an AE is incomplete, every effort will be made by the clinical team to identify and collect a valid date from the site, but in case any are incomplete, then the following rules will be used:

- If the day of the month is missing, the first of the month will be used unless it precedes the procedure date. Then the procedure date will be used.
- If the month of missing the date of the procedure will be used.
- No year is expected to be missing as the follow-up is quite short.

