Procedure Success: A patient will be considered a Procedure Success if he/she has no Major Complications (as defined above).

Unanticipated Serious Adverse Device Effect (USADE): A Serious Adverse Device Effect, which by its nature, incidence, severity or outcome has not been identified in the current version of the risk analysis report. Note: An anticipated serious adverse device effect is a serious adverse device effect which by its nature, incidence, severity or outcome has been identified in the risk analysis report.

5. Study Objectives

The following Performance Endpoints will be evaluated for the MANTA device (definitions are provided in Section 4):

1. Time to Hemostasis (Primary)

The following Safety Endpoints will be evaluated for the MANTA device (definitions are provided in Section):

1. The percentage of patients with one or more VARC-2 Major femoral vascular complications within 30±7 days following procedure (Primary)
2. The percentage of patients with one or more VARC-2 Minor femoral vascular complications within 30±7 days following procedure (Secondary)

6. Study Design

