7.8 Sponsor Representatives

Trained Sponsor personnel may perform certain study activities to ensure compliance to the clinical protocol and may provide technical expertise. Monitoring may be performed by Essential Medical and/or authorized designees according to the International Organization for Standardization (ISO) 14155 and MEDDEV guidelines for post market studies; and applicable Essential Medical standard operating procedures and work instructions. Qualified monitors will ensure investigators comply with this clinical protocol and ISO 14155 and MEDDEV post market requirements.

To ensure study personnel accept, understand and complete their assigned responsibilities, monitors, or field clinical personnel may perform periodic site visits during the course of the study. These actions will help to ensure the continued acceptability of the facilities, compliance to the clinical protocol and relevant regulations, and the maintenance of complete records.

Monitoring will include review and resolution of missing or inconsistent results and source document verification (i.e. comparison of submitted study results to original reports) to assure the accuracy of the reported data.

8. Statistical Methods

8.1. *Study Hypothesis*

This is a single arm study, and no formal hypothesis will be tested.

8.2. *Sample Size Considerations*

Up to 500 subjects are considered a meaningful sample size to assess real-world use of the MANTA device. There is no statistical basis for the sample size.

8.3. *Data Analysis*

8.3.1 *Endpoints*

The following Performance Endpoints will be evaluated for the MANTA device, definitions are provided in Section 4:

1. Time to Hemostasis (Primary)

The following Safety Endpoints will be evaluated for the MANTA device, definitions are provided in Section 4:

1. The percentage of patients with one or more VARC-2 Major femoral vascular complications within 30 ± 7 days following procedure (Primary)
2. The percentage of patients with one or more VARC-2 Minor femoral vascular complications within 30 ± 7 days following procedure (Secondary)

8.3.2 *Final Analysis*

Statistical analysis will consist of descriptive statistics using standard methods, such as mean, standard deviation, minimum/maximum, proportions, counts, etc. Two-sided 95% confidence

intervals will be calculated, when relevant. Comparison to published literature results will be descriptive only; there will be no comparative statistics.

8.4. *Interim Analysis*

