## 5.4 Safety Endpoint 3: Long-term Device Related SAEs

Objective: To quantify real-world long-term safety using the MANTA device.

Endpoint: The percentage of patients with one or more events on ipsilateral leg with MANTA device as described in the main safety endpoints beyond 30 days for each event:

- VARC-2 major complication
- VARC-2 minor complication (with no major VARC-2 complication)

Subjects to include: All subjects that have enrolled in the longer-term follow-up with a procedure attempt will be included in this analysis.

Statistical analysis (patient based): The number of subjects, percentage of patients and 95% confidence intervals for the percentage of subjects will be calculated at a minimum for subjects experiencing a major VARC2 complication and again for minor VARC2 complication.

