## 5.5 Additional Summaries

Additional summaries will be prepared similar to the effectiveness and safety endpoints using descriptive statistics. These summaries will be prepared for the overall population, by cohort (TAVR vs not TAVR), and by MANTA device size (14 or 18 Fr) at a minimum. Some summaries will be repeated for the 12M subset as appropriate.

At a minimum the following items will be included:

1. Baseline demographics and characteristics
  - Age
  - Gender
  - BMI
  - STS score (TAVR group only)
  - Medical history (prior history of PCI, CABG, Hypertension, LVEF < 20%, kidney dysfunction (GFR < 60 umol/L), pacemaker, peripheral artery disease, stroke/CVA)
  - Medications at baseline

- i. ASCAL
- ii. Oral anticoagulants
- iii. New oral anticoagulants
- iv. Clopidogrel
- v. Heparin
- vi. Other anticoagulants

2. Procedure characteristics

- Target artery characteristics
  - i. Diameter
  - ii. Calcification
  - iii. Side (left/right/both)
  - iv. Presence of scar tissue in groin on treated side
- Procedure type
- Hemostasis time (descriptive statistics and success (<10 min) – primary performance endpoints
- MANTA procedure time
- MANTA device sizes
  - i. Instances of size mismatch (where the device size exceeds the artery size)
  - ii. Sheath-to-femoral-artery ratio
- Device deficiencies
- Procedure success (proportion of subjects with no VARC-2 major complications within 30 days)

3. 30 Day Follow-up / Exit

- Average follow-up (exit date – procedure date) in days
- Medication at each time point (during procedure, post procedure, 30 day follow-up/exit)
- Summarize type of follow-up (in person/at office or via phone call)
- Reason for study exit (as reported via eCRFs).

4. 12 Month Follow-up (for subset of 100-120 subjects)

- Average follow-up (exit day of 12 month – procedure date) in days
- Provide baseline demographics for subjects that had 12M follow-up comparing to overall population.
- Target Femoral Access Site Visual Assessment
- Adverse Events occurring on MANTA side only from day 38 to 12M visit
- Medication at each time point (12month follow-up/exit)
- Reason for study exit (as reported via eCRFs)

5. Analysis of primary and secondary safety endpoints and hemostasis by on and off-label device use. On label means meeting indications per IFU.

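### SAP 6 dates any adverse event with a missing onset month to the procedure day, which removes late events from the long-term safety endpoint in SAP 5.4

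*SAP*

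**What the plan says.** **Dating.** SAP 6 first has the clinical team query the site for a valid onset date. For what stays incomplete it gives two rules. For the day: "If the day of the month is missing, the first of the month will be used unless it precedes the procedure date", in which case the procedure date is used. For the month: "If the month of missing the date of the procedure will be used" (reading the first "of" as a slip for *is*). On the year it says: "No year is expected to be missing as the follow-up is quite short". None of this distinguishes the 12-month subset.

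**Windows.** SAP 5.4, the long-term endpoint, counts "events on ipsilateral leg with MANTA device as described in the main safety endpoints beyond 30 days". SAP 5.6 item 2 agrees: "Long-term MANTA AEs (Day 31-12M) will be summarized by seriousness for subjects that participated in the extended follow-up". SAP 5.5 item 4 instead summarises "Adverse Events occurring on MANTA side only from day 38 to 12M visit". The protocol words the 30-day endpoint in two ways. Sections 5 and 8.3.1 use the visit window, as in "VARC-2 Major femoral vascular complications within 30 ± 7 days following procedure (Primary", while section 8.6 describes the primary safety endpoint as running through 30 days.

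**Adjudication.** SAP 5.4 refers back to the main safety endpoints. Under SAP 3 and 5.2 those rest on Clinical Events Committee (CEC) adjudication. Protocol 9.7 says that events identified in the 12-month extension are not adjudicated. Protocol 7.7 has sites assess VARC-2 complications at the 12-month visit.

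**The concern.** The date rules suit a 30-day study. Over 30 days, setting an unknown month to the procedure date costs little. Over 12 months the same rule gives a wrong answer for every event it touches, because an onset months later is recorded as Day 0 and fails the after-Day-30 condition. The missing-day rule does the same to some events in the second month.

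SAP 5.4 is the only long-term safety endpoint in the SAP, and it has 100-120 subjects. For a truly late event, both rules can only move the onset earlier, so they can take it out of this endpoint.

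There are two secondary consequences. A MANTA-side event on Days 31-37 can count in SAP 5.4 and 5.6 item 2 but be absent from SAP 5.5 item 4. A reader who sees the same VARC-2 labels at 30 days and at 12 months may also take both rates to be CEC-based.

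**Working it through.** The documents give no figure for this point, so there is none to reproduce. The rules were applied directly, with the procedure date as Day 0.

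**Inputs**
- Date rules: SAP 6.
- Long-term endpoint, onset after Day 30: SAP 5.4.
- Subset size 100-120: SAP 2, Table 1 footnote; Protocol 8.6.
- Procedure dates: September 2018 to July 2019, the example timeframe in Protocol 8.6 (334 dates). Checked against January 2018 to July 2019 from Protocol 6.5.6 (577 dates).
- Assumption: procedure dates are spread evenly, as are onset days where an average is taken.

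**1. Missing month.** Imputed onset = procedure date = Day 0, whatever the true day, so 100% of such late events leave SAP 5.4. Example: procedure 15 Nov 2018, event 15 May 2019 (Day 181), recorded only as 2019. SAP 6 gives 15 Nov 2018, which is Day 0 and in the wrong year. Over true onsets on Days 31-365, the year conflicts in 59,262 of 334 × 335 = 111,890 combinations (53%); with the longer enrolment period it is 46%.

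**2. Missing day.** Imputed onset = later of the first of the month and the procedure date. Example: procedure 15 Mar 2019, event 22 Apr 2019 (Day 38) becomes 1 Apr (Day 17).

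Share of procedure dates for which the imputed onset is Day 30 or earlier:

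| True onset | Sep 2018-Jul 2019 | Share |
|---|---|---|
| Day 31 | 324/334 | 97% |
| Day 37 | 258/334 | 77% |
| Day 38 | 247/334 | 74% |
| Day 45 | 170/334 | 51% |
| Day 60 | 7/334 | 2% |
| Day 61 or later | 0/334 | 0% |

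The 577-date period gives the same whole percentages. Averages: Days 31-60, 4,938/10,020 = 49%; Days 31-365, 4,938/111,890 = 4.4%. These are shares among late events whose day is missing, not probabilities that an event is lost.

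**3. What one event is worth.** 1/120 = 0.83 and 1/100 = 1.0 percentage point. With exact (Clopper-Pearson) 95% intervals at n = 110, losing the only event changes 1/110 = 0.9% (0.02-5.0%) to 0/110 = 0% (0-3.3%).

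**4. Windows.** Day 38 = 30 + 7 + 1, the day after the 30-day visit window closes. The mismatch is Days 31-37, which is 7 of the 335 days from Day 31 to Day 365 (2.1%).

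**5. What a floor on the imputed date can and cannot repair.**
- Respecting the recorded year moves the step 1 example to 1 Jan 2019 (Day 47). It does nothing when procedure and event share a calendar year, so a floor is also needed for events first recorded after the 30-day contact.
- That floor does not reach a Day 31+ event recorded at the 30-day contact itself. If visits fall evenly over Days 23-37, 8,456/9,352 = 90% of such missing-day events would still be dated Day 30 or earlier. With a contact at Day 42 (the protocol synopsis allows six weeks where that is site practice) it is 3,162/4,008 = 79%.
- In the other direction, take a true onset on Days 0-30 first reported at 12 months. The recorded month would allow a date of Day 31 or later in 48% of missing-day cases, and the recorded year would in 95% of missing-month cases.

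**The case against.** The strongest reply is that this hardly matters. The rules apply only after queries fail. The study is descriptive, with no hypothesis. Protocol 8.6 analyses 12-month events separately. A redated MANTA-related event stays in the SAP 5.6 listings with its description. The missing-day rule touches nothing after Day 60. All of this stands, and it sets the severity. It does not rescue the missing-month rule, which is wrong for every late event it is applied to.

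On the windows, Day 38 looks like a deliberate cut after the 30±7 visit window, and the endpoint and the long-term event table agree with each other. That is fair: the mismatch is confined to a supporting summary, but the SAP does not explain it.

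On adjudication, Protocol 9.7 already discloses the position, and SAP 3 ties CEC data to the primary and secondary safety endpoints, which in the protocol are the 30-day ones. What remains is a labelling gap in SAP 5.4.

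A reader might infer more than the text supports:
- *That the short-follow-up remark is the SAP's reason for all its date rules.* It explains only why no year should be missing.
- *That redated events inflate the 30-day rate.* That rate is CEC-based, and an unadjudicated 12-month event has no stated route into it.
- *That the SAP 5.4 rates cannot be produced without adjudication.* Sites assess VARC-2 complications at that visit, so a source exists.
- *That every SAP 5.4 event is unadjudicated.* A Day 31-37 event found at the ordinary 30-day visit could have gone to the CEC.

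**Conclusion.** The concern holds as a minor point. As written, the missing-month rule removes every late event it is applied to from SAP 5.4 and can contradict the recorded year. This follows from the text and needs no assumption. The missing-day rule does the same to some onsets on Days 31-60, about 4.4% of missing-day events averaged over Days 31-365 if procedure dates and onsets are evenly spread. The different start day and the absent adjudication label are secondary.

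The number of events affected is unknown, since the documents give no count of incomplete dates or of post-30-day events, but it should be small. It would be tempting to say that the 12-month rates are materially understated. The documents show only that the rules can lower them, by 0.8-1.0 point per event. The tables template mentioned in SAP 1 was not available and may settle some of this, but the SAP text does not.

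**What to change.** Change the SAP wording only.

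1. **SAP 6.** For a missing month, use the later of the procedure date and 1 January of the recorded year. For a missing day or month in an event first recorded after the 30-day contact, place the onset no earlier than the later of that contact and Day 31, where the recorded year and month allow. Flag and list every imputed onset with the visit at which it was first recorded. Report the SAP 5.4 rates twice, counting such events as long-term and as not long-term.
2. **SAP 5.4, 5.5 item 4 and 5.6 item 2.** Use one long-term start day. Day 31 matches SAP 5.2-5.4 and Protocol 8.6.
3. **SAP 5.4.** State for each event whether the CEC adjudicated it. Label those identified in the 12-month extension as site-assessed and unadjudicated, citing Protocol 9.7, and do not apply one blanket label.

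The floor has a price. A true onset at Day 30 or earlier that was first reported after the 30-day contact may be counted as long-term. A Day 31+ event first recorded at a 30-day contact held on Day 31 or later gets no floor. The listing and the two-way count must cover both cases.

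The cost is SAP text, minor programming and a short listing. No new data, CEC work or protocol amendment is needed.
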